PK subjects will come to the site on Day 1 of randomization ON AN EMPTY STOMACH and return their unused study drug at that time point. They will receive the first dose of medication at the site following the first PK blood draw, and complete the questionnaires listed below. PKs will also be performed at 1, 2, 4, and 8 hours post-dose. A sample for liver function tests will be drawn with the 8-hour post-dose PK draw. They will receive 4 daily doses to take home, then return on Day 6 to receive their 6th dose at the site after their first PK draw of the day. PKs will again be obtained post-dose at 1, 2, 4 and 8 hours, a sample for liver function tests will be drawn with the 8-hour post-dose PK draw, and all the questionnaires completed.

Following the 5-7 day course on the pro-kinetic dose, ALL patients will be randomized to drug or placebo and enter Period 4. Randomization will be 1:1 to treatment vs. placebo. Randomization will occur in accordance with the randomization schedule generated by [name] at Weill-Cornell Medical College. Patients and study staff will be blinded to actual study treatment and will remain blinded throughout the remainder of the study. BDI, MMSE, Trail making A and B, NMSQ, UM-PDHQ, PFS-16, RBDQ, PDSS, PAC-SYM and PAC-QOL will be administered prior to randomization. The UPDRS will be administered and weight and vital signs will be taken).

Assuming randomization is to treatment group, the patient will remain on that dose daily for a 6 day period (6 dosing days). Patients randomized to placebo will be switched to the same number of placebo tablets as they were taking prior to switching. All patients will continue to keep daily diaries during this period. The use of rescue medication (suppositories and enemas) for constipation will be permitted as needed if a bowel movement has not occurred for 3 days and recorded in the diary. Patients will be contacted daily. The suppository will be taken on the evening of the third day as shown in Figure 1 above. *Any bowel movement produced as a result of rescue medication will not be counted.*

Patients reaching their tolerability limit at a dose lower than a clinically effective dose (STDE) will be terminated from the study. We have included 40 patients in this Stage to allow for 15% drop-outs for reasons including tolerability.

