4.3 Tolerability Evaluations

Tolerability will be measured by the following DLT endpoints: Dose Limiting Toxicity (DLT) will be the dose which induces repeated vomiting, diarrhea, abdominal pain or symptomatic postural hypotension within 24 hours of dosing. It is defined using the Common Terminology Criteria for Adverse Events (CTCAE) as:

- Recurrent vomiting: 3-5 episodes of vomiting within 24 hours of taking ENT-01 (i.e., 3-5 episodes of Grade 2 vomiting)

- Recurrent diarrhea: 4-6 episodes of diarrhea within 24 hours of taking ENT-01 (will be recoded as a Grade 2 diarrhea)
- Moderate Abdominal pain that limits instrumental activities of daily living within 24 hours of taking ENT-01 (Grade 2 AE)
- postural hypotension including Moderate dizziness, lightheadedness or fainting upon rising from lying to sitting or standing and severe enough to require medical intervention within 24 hours of taking ENT-01 (Grade 2 AE) or either a systolic blood pressure less than 80mmHg or diastolic blood pressure less than 40mm Hg

In addition, the following will also be considered dose limiting toxicity for the purpose of analyses:

- Elevation of LFTs > 3 times the upper limit of normal (ULN)
- A reduction of body weight of 10% or more

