7.8.6 Analysis of Tolerability Data

Stage 1 and up to end of fixed dosing period in Stage 2

Tolerability will be measured by DLT endpoints defined in Section 4.3.

The frequency of each tolerability endpoints including recurrent vomiting, recurrent diarrhea, abdominal pain and postural hypertension, and etc. will be summarized by dose (Stage 1) or for treatment period (Stage 2). Percentages will be based on the number of subjects in each dose level (Stage 1) or the number of subjects (Stage 2) in the safety population.

Randomization period in Stage 2

Additionally, the above summaries will be provided during the randomization period by treatment for randomized population.

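### The by-arm DLT table in SAP 7.8.6 uses symptom criteria timed from ENT-01 intake, so, applied as itemized, events after the switch to placebo go almost entirely uncounted

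*SAP*

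**What the plan says.** SAP 7.8.6 states "Tolerability will be measured by DLT endpoints defined in Section 4.3". It tabulates the frequency of each endpoint and then extends the tables to the randomized period: "Additionally, the above summaries will be provided during the randomization period by treatment for randomized population". It gives no separate definition for that second set of tables.

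SAP 4.3 first describes a DLT as a dose that induces the listed symptoms within 24 hours of dosing, and then says how it is defined, item by item:
- "Recurrent vomiting: 3-5 episodes of vomiting within 24 hours of taking ENT-01"
- "Recurrent diarrhea: 4-6 episodes of diarrhea within 24 hours of taking ENT-01"
- moderate abdominal pain, with the same ENT-01 window
- postural hypotension, with a symptom limb that carries the same ENT-01 window and a second limb that does not: "or either a systolic blood pressure less than 80mmHg or diastolic blood pressure less than 40mm Hg"

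Liver-test elevation and weight loss are added without any time window.

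On the placebo arm, Protocol Section 3.1 (Period 4) says: "Patients randomized to placebo will be switched to the same number of placebo tablets as they were taking prior to switching". SAP 2.3 says the same.

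**The concern.** A table by arm is informative only if the same event is scored the same way in both arms. Here the symptom criteria name the active drug as the start of the clock. A patient on placebo takes none of it during the six randomized days. Grade 2 diarrhea a few hours after a blinded tablet would therefore be a DLT if the tablet was ENT-01 and not a DLT if it was placebo.

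Tolerability is part of the Stage 2 primary objective (SAP 3.2.1), and the amended SAP keeps this by-arm table. If the items are programmed as written, the ENT-01 column shows the whole event rate, the placebo column shows close to none, and the contrast reads as a drug effect even where there is none.

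**Working it through.** The plan states no DLT rate, so there is no figure to reproduce. The check compares the text of the criteria with the table they feed.

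**Step 1. Which criteria can be met after the switch to placebo, as itemized in SAP 4.3?**

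| Criterion | Clock starts at | Countable on placebo? |
|---|---|---|
| Recurrent vomiting | ENT-01 intake | essentially no |
| Recurrent diarrhea | ENT-01 intake | essentially no |
| Abdominal pain | ENT-01 intake | essentially no |
| Postural hypotension, symptom limb | ENT-01 intake | essentially no |
| Postural hypotension, blood-pressure limb | none stated | yes |
| Liver tests above 3 times ULN | none stated | yes |
| Weight loss of 10% or more | none stated | yes |

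Protocol 10.1.1 does attach a window to the liver-test criterion. SAP 4.3, which 7.8.6 cites, does not, and SAP Section 1 says that the SAP supersedes the protocol's statistical considerations.

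**Step 2. How much of the last open-label window is left?** All patients take ENT-01 daily up to randomization, on awakening (Protocol 3.1, Periods 3.2 and 4). The 24 hours after the last open-label dose therefore end at about the first blinded dose. Any remainder is short, and an event in it follows ENT-01 rather than placebo.

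**Step 3. Which anchor applies?** The introductory sentence of 4.3 times the window from dosing, which could include placebo tablets. The items that follow are presented as the definition and name ENT-01, as do Protocol 9.8 and 10.1.1. The two parts of 4.3 give different placebo counts, and 7.8.6 does not choose between them.

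**Step 4. Direction and size.** Let q_E and q_P be the true probabilities of one symptom endpoint over the six days.
- Neutral window: expected difference = q_E − q_P.
- ENT-01 window: expected difference ≈ q_E − 0.
- Bias = q_E − (q_E − q_P) = q_P, always against ENT-01. With q_E = q_P = q, the row shows about q against 0.

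The documents do not give q. As an illustration only, for a single row, the expected number of placebo events left out is n × q, and the chance of at least one is 1 − (1 − q)^n:

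| Assumed q | n = 20: expected; chance of at least one | n = 10: expected; chance of at least one |
|---|---|---|
| 5% | 20 × 0.05 = 1; 64% | 0.5; 40% |
| 10% | 2; 88% | 1; 65% |
| 20% | 4; 99% | 2; 89% |

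The 20 per arm is the planned size in Protocol 2.2. The 10 is an assumed smaller arm. SAP 2.1 records that the February 2018 amendment removed the randomization period, and the SAP does not state the resulting arm size.

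**Step 5. Comparison with the adverse event tables.** SAP 7.8.1 summarizes adverse events in the randomized period by treatment, and counts an event as treatment-emergent from the start of a treatment to the start of the next. That rule is the same for both arms. A placebo patient's Grade 2 diarrhea could thus appear in the 7.8.1 tables and be absent from the 7.8.6 table.

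**The case against.** The strongest reply has four parts.

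- **The text does not force a zero.** A reader might infer that the placebo symptom DLT rate is zero by construction. The introductory sentence of 4.3 refers to dosing, so a programmer could legitimately count placebo doses. This stands: the near-zero count follows from the itemized criteria, not from every reading of 4.3. It does not remove the point, because a section that supports two placebo counts needs one stated rule.
- **Other by-arm safety tables exist.** A reader might take this to be the trial's only placebo-controlled look at tolerability. It is not. SAP 7.8.1 covers adverse events by treatment, and 7.8.2 to 7.8.5 provide for randomization-period summaries of other safety data. A placebo event recorded as an adverse event would be missing from one table, not from the report. This also stands.
- **Nothing inferential rests on the table.** No between-arm DLT test is planned, SAP 7.7 drops formal between-arm comparisons for the pharmacodynamic variables because of the small sample, and patients and staff are blinded in Period 4, so recording at site is not affected. The asymmetry would enter only at tabulation. This limits the consequence.
- **The illustration uses assumed rates.** It does, and it must not be read as a pooled result: 7.8.6 reports each endpoint separately, and the postural hypotension row can exceed zero on placebo through its blood-pressure limb.

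**Conclusion.** The point holds in a limited form. SAP 4.3 times its itemized symptom criteria from ENT-01 intake and its introductory sentence from dosing, and 7.8.6 uses the section by arm without resolving the difference. Followed as itemized, the vomiting, diarrhea and abdominal pain rows, and the symptom part of the postural hypotension row, omit virtually all placebo-period events, so the table is biased against ENT-01 by the placebo event rate. That conclusion assumes that the items, rather than the introductory sentence, are programmed, and that daily dosing leaves little of the last open-label window.

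The size cannot be derived from the documents. It is about q against 0 for an affected row with equal true rates, with q and the actual arm size both unstated. The documents do not support the stronger inferences that placebo counts must be zero under any reading, that placebo events vanish from the report, or that the trial's placebo-controlled safety comparison as a whole is invalid. The reference in 7.8.6 to postural hypertension, where 4.3 defines hypotension, is a clerical slip and adds no weight.

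**What to change.** In SAP 4.3 and 7.8.6, state one anchor for the randomized-period table: the event occurs within 24 hours of taking blinded study drug (ENT-01 or placebo), applied identically in both arms. Say that this governs tabulation only, so that no clinical rule in the protocol changes. In 7.8.6, correct postural hypertension to match 4.3.

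The cost is a few words in the SAP and the matching programming specification. No new data are needed: the diary records the date and dose of study medication (Protocol 2.2), and adverse event recording includes the date of onset (Protocol 9.12). The documents do not show that onset clock times are collected, but the re-anchored window needs no more timing detail than the existing 24-hour rule.

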7.8.7 Extent of Exposure

For Stage 1, dose administration details by subject will be listed.

For Stage 2, number of subjects and percentage on each dose level will be presented for period 3.2. The denominators for percentages will be based on the number of subjects in the Safety Population. For each dose period, total dose (mg), extent of exposure (days), and applicable compliance (%) captured on the eCRF page will be summarized using descriptive statistics.

7.8.8 I-BUTTON

I-Button data will be analyzed by a separate group. The data will not be included in this SAP.

7.9 Additional Data Presentation as Listing

Additional data listings will be provided for the following information as appropriate:

- Subject eligibility
- Medical history
- Constipation history
- Stool diary
- Sleep diary
- Individual questions from questionnaires:
 - NMSQ
 - BDI-II
 - MMSE
 - UM-PDHQ
 - PFS-16
 - PAC-SYM
 - PAC-QoL
 - RBDQ
 - UPDRS
 - ROME-IV
 - Trail make A
 - Trail make B
 - PDSS

8 DEFINITIONS AND CONVENTIONS FOR DATA HANDLING

8.1 Definition of Baseline

For all evaluations unless otherwise noted, baseline is defined as the most recent measurement prior to the first administration of study drug in Stage 1. Baseline can be the same date as first dose, given the measurement is expected prior to first dose when only date information is available.

8.2 Analysis Visit Window

For safety parameters excluding clinical laboratory data, measurements collected from unscheduled visits will not be included in the by-visit summary tables but will be included in the listings. Early termination visits for safety measurements will not be mapped to any scheduled post-baseline visit, but will be used as the last assessment during treatment period.

8.3 Pharmacodynamic Data Handling

All PD parameters from questionnaires will follow instructions or manuals coming in with them. If any special handling rules were needed, they would be documented in ADaM data specifications.

For PD parameters from diary data, generally, there will be no imputation for missing diaries. However, if there were some partial dates or times not in 24-hour clock present in diary data, they might be imputed in order to derive PD parameters, using common sense. These details of handling rules would be documented in ADaM data specifications.

8.4 Safety Data Handling

For all safety data, only observed data will be used for analyses, and missing data will not be imputed.

8.5 Handling of Repeated Clinical Laboratory Tests

For laboratories results at unscheduled visits, it will be treated as repeated laboratory results for the closest previous visit. The last repeat of laboratory results will be used in the summary tables for that visit. All the laboratory test results (original test results and repeated results) will be included in the data listings.

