MTD: Maximum Tolerated Dose **ID: Intolerant Dose** No prokinetic response MTD ID Day10 Day13 Subject Day 1 Day4 Day7 Day16 Day19 Day22 Day 25 25mg 50mg 100mg 75mg >125mg 150mg 175mg 2 25mg 50mg 75mg 100mg 125mg 150mg 175mg 200mg Stage 1 Period 2.1 3 50mg 75mg 100mg 125mg 150mg 175mg 25mg (COHORT 1) 4 25mg 50mg 75mg 100mg 125mg 150mg Single dose 125mg 5 25mg 50mg 100mg 150mg 75mg 175mg 200mg safety, 50mg 100mg 125mg 6 75mg 25mg tolerability and 50mg 100mg 7 25mg 75mg 125mg 150mg 175mg identification of 8 25mg 50mg 75mg 100mg 125mg 150mg prokinetic dose 50mg 100mg 125mg 150mg 25mg 75mg → 175mg 200mg 10 25mg 50mg 75mg 100mg 125mg 150mg 175mg 200mg STDE DOSE in this example is 75 mg, that being the lowest dose that is safe and tolerable in all subjects and has a prokinetic effect in at least some

Schematic for Stage 1, Period 2.1: Hypothetical dosing regimens

Pharmacokinetics: Timed blood samples (5.0 mL) will be collected into Li-Heparin treated tubes for analysis of ENT-01 plasma concentrations. Plasma samples will be obtained for pharmacokinetics before dose administration and at 1, 2, 4, 8, and 24 hours.

Once collected, PK samples will be stored in a -20°C or -70°C freezer until time of shipment. Labels and appropriate shipping materials will be provided to sites. The concentration of study drug will be determined from the plasma samples using a validated analytical method. Details of the method validation and sample analysis will be included with the final clinical study report.

Individual stopping criteria:

The complete panel of Blood Chemistries described in Appendix 1 are to be drawn 24 hours after each dose. Results will be reviewed the evening before the following dose. In addition, any patient with at least 1 DLT endpoint (see **Section 9.8**), or with another non-DLT gastrointestinal AE > grade 3 that is at least possibly attributable to ENT-01, or elevated AST, ALT, or total bilirubin > 3x ULN or a reduction of body weight of 10% or more from baseline will be terminated. ENT-01 has very little systemic absorption, and hence adverse events are expected to be within the gastrointestinal system.

Refer to Section 9.12 for Adverse Event Grading and to Section 9.8 for DLT Endpoint

Criteria.

Go/No-go decision:

Safety: We are assuming that no more than 1 patient out of ten (10%) will have an adverse event

of grade 4 or 5 that is at least possibly related to ENT-01 in dose levels thought to be below

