9.11 Laboratory Abnormalities

Clinical labs will be performed by a local laboratory. Labs to be drawn during the study include: serum chemistries, a hematology panel and urinalysis. A serum pregnancy test must be performed and the result must be negative prior to the entry of women of child bearing potential. The investigator must obtain verification that the local laboratory meets the standards for quality and consistency set by the College of American Pathologists.

Clinical laboratory reports must be reviewed by a physician for out-of-range values within 24 hours of receipt. Out-of-range values will be evaluated using the following notations:

- NS Not clinically significant
- LE Laboratory Error
- PT Patient abnormal; relates to the patient's usual state of health
- SG Significant, other. This value cannot be explained by any of the other flags.

By definition a lab value flagged as "SG" must be entered on the adverse clinical laboratory event page in the case report form. A laboratory test flagged "SG" must be repeated as soon as possible. The investigator may use his/her own judgment as to whether the abnormal finding is sufficient reason to immediately withdraw the patient from the study.

If a laboratory value is considered to be serious and life-threatening the patient should be immediately discontinued from the study and appropriate therapy started. Refer to sections **9.7-9.12** for definition of a serious adverse event and related terms, and to sections **9.13-9.16** for details on reporting a serious adverse event.

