An assessment of normal or abnormal will be recorded and if the EKG is considered abnormal, the abnormality will be documented on the CRF. EKGs will be repeated if clinically significant abnormalities are observed or artifacts are present.

Laboratory Assessments

Laboratory assessment samples are to be obtained at designated visits as detailed in the Schedule of Procedures and Assessments.

All clinically significant laboratory values should be captured on the CRF as AEs.

Blood and urine samples will be analyzed at the laboratory facility at the Investigational site. Urine samples will be analyzed by dipstick, and a microscopic analysis will be performed if the results of dipstick indicate abnormalities to be further investigated. All laboratory reports must be reviewed, signed, and dated by the Investigator. A legible copy of all reports must be filed with both the patient's CRF and medical record (source document) for that visit. Any laboratory test result considered by the Investigator to be clinically significant should be considered an AE (clinically significant AEs include those that require an intervention). Clinically significant abnormal values occurring during the study will be followed until repeat test results return to normal, stabilize, or are no longer clinically significant.

Adverse events

All reported AEs will be coded using the CTCAE version 4.03 terminology. The incidence of treatment-emergent AEs (TEAEs; events with onset dates on or after the start of the study drug) and treatment-related AEs will be summarized by system organ class (SOC) and preferred term

(PT). Events with missing onset dates will be included as treatment-emergent. If a patient experiences more than 1 occurrence of the same AE, the occurrence with the greatest severity and the closest association with the study drug will be used in the summary tables. SAEs and AEs that result in treatment discontinuation will be summarized. In addition, AEs of special interest will be summarized by SOC and PT; categories of AEs of special interest include: nausea, vomiting, abdominal pain, diarrhea, and rectal bleeding.

All AEs will be listed by patient, along with information regarding onset, duration, relationship and severity to study drug, action taken with study drug, treatment of event, and outcome.

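### SAP 8.5 tabulates the last repeat of a laboratory test without an on-treatment limit, which biases the laboratory frequency and shift tables towards less abnormal results

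*SAP*

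**What the plan says.** **Selection rule.** Under SAP 8.5, for a laboratory result from an unscheduled visit, "it will be treated as repeated laboratory results for the closest previous visit". The next step is "The last repeat of laboratory results will be used in the summary tables for that visit". The section sets no time limit after the last dose, does not require the original to be in error, and does not keep the worst value. It does preserve the data: "All the laboratory test results (original test results and repeated results) will be included in the data listings".

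**Tables that use it.** SAP 7.8.2 plans frequencies (low/normal/high or normal/abnormal) by period and shifts from baseline by period. It plans no worst-value table and no laboratory table at a multiple of ULN.

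**What generates repeats.** Protocol 9.11 says that a value flagged SG (significant) "must be repeated as soon as possible". Protocol 10.3.1 says that clinically significant abnormal values "will be followed until repeat test results return to normal, stabilize, or are no longer clinically significant".

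**What stops drug.** In Stage 1 (Protocol 3.1, Period 2.1) the individual stopping criteria include "or elevated AST, ALT, or total bilirubin > 3x ULN". The Stage 2 criteria (Period 3.2) also terminate patients for liver tests above 3x ULN.

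**The concern.** A last-repeat rule does little harm when repeats correct technical faults. Here the trigger for a repeat is an abnormal value, and the end of follow-up is recovery or stability. Selecting the last result therefore selects, on average, a less abnormal one. After a liver-test stop, that result also comes from a patient no longer taking the drug, yet it is filed under the dosing visit.

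Safety is the Stage 1 primary objective and part of the Stage 2 primary objectives. The laboratory tables are the one tabulated summary that does not depend on an investigator judging a value clinically significant. If they lean towards normal, a reader of the study report sees fewer on-drug abnormalities than were measured.

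**Working it through.** The plan gives no figure to reproduce here. The check applies the rule to one subject and then scales the result.

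**Step 1: one subject.** The ALT values are assumed, in multiples of ULN; above 1 counts as High.

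| Sample | Scheduled? | On drug? | ALT |
|---|---|---|---|
| Run-in | yes | no | 0.8 |
| 24 h after dose, drug then stopped | yes | yes | 3.6 |
| Repeat 1 | no | no | 3.2 |
| Repeat 2 | no | no | 1.8 |
| Repeat 3 | no | no | 0.9 |

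The three repeats belong to the dosing visit under SAP 8.5. The entry for the dose period is then:

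- last repeat (SAP 8.5): 0.9, shift Normal to Normal;
- original scheduled result: 3.6, shift Normal to High;
- worst on-drug result: 3.6, shift Normal to High.

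If follow-up had ended at repeat 2 because the value was judged stable, the entry would be 1.8 and the shift would still be Normal to High. The category is lost only when the last repeat falls back within range.

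**Step 2: scale.** If k subjects follow the pattern in Step 1 and all recover, the High row loses 100 × k/n percentage points:

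| n | k = 1 | k = 2 | k = 3 |
|---|---|---|---|
| 10 (Stage 1) | 10.0 | 20.0 | 30.0 |
| 34 (Stage 2 evaluable target) | 2.9 | 5.9 | 8.8 |
| 40 (Stage 2 enrolled) | 2.5 | 5.0 | 7.5 |

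As an assumed illustration, with k = 2 in Stage 1 the table would show 0/10 High (exact 95% CI 0 to 30.8%) instead of 2/10 (2.5 to 55.6%). SAP 7.8.2 does not say how a subject's several Stage 1 dosing visits are combined into one dose period; these figures assume one entry per subject.

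**Step 3: room for replacement.** In the amended Stage 2 schedule (SAP Table 4), chemistry and haematology are drawn at Visit 1, at Visit 3 (Day 4 of the fixed-dose period, the last day shown) and at Visit 4 (washout Day 14). Visit 3 is the only scheduled on-treatment draw. An unscheduled repeat taken between Visits 3 and 4 would replace it, whether or not the patient had been stopped. A sample drawn at the scheduled washout visit belongs to washout and replaces nothing.

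**Step 4: what else records the event.**

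| Output | Covers | Gap |
|---|---|---|
| Listings (SAP 8.5) | every result | no rates |
| TEAE tables (SAP 7.8.1) | values recorded as adverse events under Protocol 10.3.1 | needs a judgement of clinical significance |
| DLT table (SAP 4.3, 7.8.6) | liver tests above 3x ULN | no smaller liver-test rises and no other analyte; the result that feeds the count is not stated |

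On the last gap, Protocol 10.1.1 ties the liver-test DLT to the 24 hours after dosing, while the matching item in SAP 4.3 gives no window.

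**The case against.** A reader might infer that SAP 8.5 removes from the report's tables the very abnormalities that stopped treatment, and always puts a normal value in their place. The documents do not support that, for four reasons.

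- A liver test above 3x ULN is a DLT for analysis, tabulated by dose in Stage 1 and for the treatment period in Stage 2. The 24-hour window in Protocol 10.1.1 points to the post-dose value, which a later repeat could not cancel. Both subjects in the 2/10 illustration should appear there.
- Clinically significant values are to be recorded as adverse events, and SAP 7.8.1 tabulates these by maximum grade, by relationship and by whether they led to discontinuation.
- Follow-up may end at stability, so the last repeat can still be High. A repeat that is worse would move the table the other way.
- Stopping, the safety hold and the safety board's review are not tied to SAP 8.5, and the affected tables carry no test or decision rule.

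The protocol also expects low plasma concentrations after oral dosing, so the counts in the illustration should not be read as a forecast. All of this stands, and it limits the reach of the problem. It does not remove the bias from the SAP 7.8.2 tables, and smaller liver-test rises and other analytes have no DLT table behind them.

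A reader might also extend the argument to vital signs and ECGs through SAP 8.2, where early-termination measurements "will be used as the last assessment during treatment period". That extension is weak. The individual stopping criteria contain no ECG item, and the blood-pressure and weight criteria are counted as DLTs. What remains is a small inconsistency: a measurement made after drug has stopped is labelled as treatment period.

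**Conclusion.** The concern holds for the laboratory frequency and shift tables of SAP 7.8.2 and does not extend beyond them. Read with the protocol's repeat-testing and stopping text, SAP 8.5 allows an on-drug abnormality to be overwritten by an off-drug value. The direction is systematic, towards less abnormal, but not invariable.

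Each affected subject who recovers to normal costs the High row 10 points in Stage 1 or 2.5 points in Stage 2. This rests on follow-up samples being unscheduled, on the last one being within range, and on one table entry per subject per period. The documents give no expected number of such subjects.

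This should be fixed before database lock. Because the listings, TEAE tables and DLT table provide partial cover, it is not a defect that undermines the safety conclusions by itself.

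**What to change.** 1. **SAP 8.5:** tabulate the original scheduled result by visit. Let a repeat replace it only when the original carries the LE (laboratory error) flag of Protocol 9.11.
2. **SAP 7.8.2:** add, for each period, a worst on-treatment value and a shift table based on it, using scheduled and unscheduled results up to a stated time after the last dose.
3. **SAP 4.3 and 7.8.6:** state that the count of liver tests above 3x ULN uses all post-dose results, and reconcile its time window with Protocol 10.1.1.
4. **SAP 8.2 (minor, for consistency):** assign early-termination measurements to treatment or washout by days since the last dose.

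The cost is SAP wording and a little more programming. SAP 8.5 already lists original and repeated results, so no new data are needed. Tabulated abnormality rates may be somewhat higher.
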